5.4 Dose Delays and Modifications

The Investigator may suspend ADCT-402 dosing for up to 21 days for any patient who experiences a protocol-defined DLT after Cycle 1 (the defined DLT observation period). At the discretion of the Investigator, the dose may also be delayed for up to 21 days for any toxicity that does not meet DLT criteria. Resumption of dosing with ADCT-402 after suspension is at the discretion of the Investigator, based on assessment of the patient's clinical condition and whether or not the patient is deriving potential clinical benefit from treatment with ADCT-402. Following recovery to Grade 1 or to baseline grade, treatment with ADCT-402 may resume at the Investigator's discretion.

Patients who resume treatment following a dose delay may, at the discretion of the DESC, have their dose of study drug reduced by 50%. If toxicity occurs again at the reduced dose, the patient will be discontinued from the study.

During part 2, dose delay due to toxicity may extend beyond 21 days at the discretion of the investigator, in consultation with the Sponsor, based on assessment of the patient's clinical condition and whether or not the patient is deriving potential clinical benefit from treatment with ADCT-402. When dosing is resumed, the dose may be decreased by 50% at the discretion of the Investigator, in consultation with the Sponsor.

If the dose is reduced and the toxicity recurs, the dose will be further reduced by 50%.

If toxicity recurs after second dose reduction, study drug must be discontinued permanently.

If dose is held for six weeks or more, restaging scans must be done prior to restarting dosing to rule out disease progression.

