4.2.1 Reasons for Withdrawal/Discontinuation

Patients may withdraw from the study at any time and for any reason without prejudice to their future medical care by the Investigator or others at the study site.

A patient may be withdrawn from treatment with ADCT-402 for any of the following reasons:

- Disease progression.
- AE.
- Withdrawal of consent.
- Major protocol deviation.
- Required treatment delay >21 days (except in case of potential patient benefit, which must be approved by the Sponsor).
- Following a dose delay due to toxicity, if the same toxicity recurs after second dose reduction, study drug must be discontinued permanently.
- Non-compliance, including lost to follow-up.
- Pregnancy.
- Other (e.g., development of contraindications with use of the study drug).
- The Investigator determines that it is in the best interest of the patient to discontinue the patient's participation in the study.
- Discontinuation of the study by the Sponsor.

- Death.

Patients experiencing other significant toxicities must be immediately and permanently withdrawn from treatment with ADCT-402 as follows:

- Any patient who experiences a Grade 3 or higher hypersensitivity ([Appendix 12.3](#)) reaction, regardless of premedication, during any cycle of treatment.
- Any patient who experiences a recurrent Grade 3 or 4 toxicity, excluding hematological toxicity.
- Any patient who requires a dosing delay >21 consecutive days from the planned Day 1 dosing at any time during treatment (except in case of potential patient benefit, which must be approved by the Sponsor).

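### Protocol 5.4 prescribes a second dose cut for any recurrent toxicity, while 4.2.1 requires permanent withdrawal if that toxicity is Grade 3 or 4 and non-hematologic

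*Protocol*

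**What the plan says.** Protocol 5.4 covers dose delays and reductions. It opens with DLTs after the observation period: "The Investigator may suspend ADCT-402 dosing for up to 21 days for any patient who experiences a protocol-defined DLT after Cycle 1". It also allows delays for toxicity that is not a DLT. Going back on drug is optional: "Resumption of dosing with ADCT-402 after suspension is at the discretion of the Investigator".

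Two reduction rules follow.

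- **Single-reduction rule.** A paragraph with no Part label lets the DESC halve the dose after a delay. If toxicity occurs again at that dose, the patient is discontinued.
- **Two-reduction rule.** A paragraph that begins with Part 2 permits longer delays and adds "When dosing is resumed, the dose may be decreased by 50% at the discretion of the Investigator, in consultation with the Sponsor". The next line, on its own and unlabelled, reads "If the dose is reduced and the toxicity recurs, the dose will be further reduced by 50" percent. The line after that reads "If toxicity recurs after second dose reduction, study drug must be discontinued permanently".

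Protocol 4.2.1 has two lists. The first gives reasons for which a patient may be withdrawn, and it repeats the two-reduction stop: "Following a dose delay due to toxicity, if the same toxicity recurs after second dose reduction, study drug must be discontinued permanently". The second is mandatory: "Patients experiencing other significant toxicities must be immediately and permanently withdrawn from treatment with ADCT-402". One of its three triggers is "Any patient who experiences a recurrent Grade 3 or 4 toxicity, excluding hematological toxicity". That trigger has no exception for Part 2 or for patients already on a reduced dose.

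**The concern.** For one class of event, the two sections give an Investigator who wants to continue dosing different instructions. The second cut in 5.4 is worded as what will happen and has no limit by grade or organ class. The stop in 4.2.1 is worded as what must happen. Neither section refers to the other on this point.

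A site working from the dose-modification section alone could therefore re-dose a patient whom 4.2.1 says must come off treatment. Safety and tolerability in Part 2 is a primary objective, so the stopping rule there should have only one reading. Reporting is a smaller matter: sites that read the rules differently would record different actions for the same clinical event.

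**Working it through.** The plan gives no figure to reproduce. The check compares the rules and then works out the dose that would be given.

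**Does this class of toxicity fall under 5.4?** Yes. Section 5.4 covers protocol-defined DLTs after Cycle 1. The non-hematologic DLT list in Protocol 6.3.1 includes adverse events of Grade 3 or higher, and Protocol 3.2 applies the same criteria in Part 2.

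**Where do the rules disagree?** They are compatible for recurrent hematologic toxicity and for recurrent non-hematologic toxicity of Grade 2 or lower, because the mandatory trigger in 4.2.1 does not reach those events. They disagree only for recurrent non-hematologic Grade 3 or 4.

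**When does treatment stop for that class?** Count occurrences, with the dose halved after the first.

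| Rule | 1st occurrence | 2nd occurrence | 3rd occurrence |
|---|---|---|---|
| 4.2.1 mandatory list | may continue | permanent stop | – |
| 5.4 single-reduction rule | delay, cut to 50% | stop | – |
| 5.4 two-reduction rule | delay, cut to 50% | cut to 25% | permanent stop |

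The gap is 3 − 2 = 1 occurrence, and only if the two-reduction rule governs. Its position directly after the Part 2 paragraph suggests that it is the Part 2 rule and that the single-reduction rule belongs to Part 1, but 5.4 does not say so. If the single-reduction rule applied throughout, it would agree with 4.2.1 on when to stop, and the contradiction would lie inside 5.4.

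**What dose would be given?** Two cuts leave 0.5 × 0.5 = 0.25 of the dose to which they are applied. The Part 2 regimens are those listed in Protocol 3.1.

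- Regimen A (constant dose every 3 weeks): 0.25 × 90 = 22.5; 0.25 × 120 = 30; 0.25 × 150 = 37.5; 0.25 × 200 = 50 µg/kg.
- Regimens B to E: a twice-reduced dose cannot be given before the third infusion (full dose, first cut, second cut). By then the scheduled dose is 60 µg/kg, after two infusions in B, C and D and after one in E. Applied to the scheduled dose, the cuts give 0.25 × 60 = 15 µg/kg. Applied to the starting dose, they give 30 (B), 37.5 (C) or 50 (D and E) µg/kg. Section 5.4 does not say which dose is meant.

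These are doses a patient would receive. They do not measure harm.

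**What moves in the tables?** The overview in SAP 4.8.2.1 counts events and patients, with one row for events leading to delay or reduction and one for events leading to permanent withdrawal. A patient who reaches the conflict has already had a reduction for the first episode and so, if that was recorded as the action taken, is already in the delay-or-reduction patient count. What can change is the withdrawal row, with its breakdown by preferred term, and the event-level counts.

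**The case against.** The best defence is that the rules are nested. The two-reduction stop sits in the permissive list of 4.2.1, and the mandatory list that follows is introduced as covering other significant toxicities. Section 5.4 would then be the general step-down and 4.2.1 a stricter exception for non-hematologic Grade 3 or 4. Two details support this. The limit on delays over 21 days in the mandatory list has an exception for patient benefit with Sponsor approval, while the recurrent Grade 3 or 4 trigger has none, which looks deliberate. Grade 3 or higher hypersensitivity is also a DLT that ends treatment under 4.2.1, and 5.4 does not repeat that stop either.

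Much of this stands, and 4.2.1 is probably the controlling rule. But the reader has to infer it. The hypersensitivity parallel is weaker than it looks: Protocol 5.2 states that stop a second time, and the suspension language in 5.4 is permissive, whereas the second cut is not. The permissive list in 4.2.1 also repeats the two-reduction stop without a grade limit, so turning to 4.2.1 does not fully settle the matter.

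Oversight also limits the exposure. Part 2 reductions are made in consultation with the Sponsor, and Protocol 6.3.1.1 keeps the DESC in place during Part 2.

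A reader might infer that 5.4 compels re-dosing. It does not, because resumption and the first reduction are discretionary. A reader might also infer that the safety tables would be wrong. They would not: they tabulate the action taken and are correct under either rule.

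**Conclusion.** The inconsistency is real but minor. Sections 5.4 and 4.2.1 differ for recurrent non-hematologic Grade 3 or 4 toxicity, and 5.4 does not say that 4.2.1 prevails. If the two-reduction rule is the Part 2 rule, a Part 2 patient who continues under it could receive at least one infusion that 4.2.1 forbids, at 25% of the starting dose on regimen A and possibly as low as 15 µg/kg on regimens B to E.

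This rests on the inferred split of 5.4 by Part. It also requires a patient who has such a toxicity, recovers, resumes at a reduced dose and then has a recurrence at Grade 3 or 4. The documents give no rates for that sequence, so the number affected cannot be derived. It is zero if every Investigator stops at recurrence.

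Two stronger readings are not supported. One is that dose finding is compromised: the MTD rests on DLTs in Cycle 1 of Part 1, and the conflict arises only after an earlier episode, a delay and a reduction, so MTD and DLT evaluation is unaffected. The other is that 22.5 to 50 µg/kg describes Part 2 as a whole: as doses certain to follow from two cuts, those figures fit regimen A only.

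**What to change.** Make two changes to 5.4 together.

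1. Add to the second-reduction sentence: *except recurrent Grade 3 or 4 non-hematologic toxicity, which requires permanent withdrawal from treatment (Section 4.2.1)*.
2. Label the single-reduction rule as Part 1 and the two-reduction rule as Part 2. Without the labels, the two rules in 5.4 still give different stopping points.

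If the sponsor does intend dose-reduced Part 2 patients to continue after such a recurrence, the exception belongs in the mandatory list of 4.2.1 instead, and the labels are still needed.

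The cost is one clause and two labels. Protocol 10.2.1 requires an amendment with the usual approvals, so this can go into the next one. It adds no visits, data or patients, and the SAP needs no change.

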5.5 Identity of Investigational Product

ADC Therapeutics will provide and distribute adequate supplies of ADCT-402 to the study sites. The following drug supplies will be used in the study:

Product	Supplied As:
ADCT-402	10-mL single-use glass vial with overfill to allow for up to 3.2 mL to deliver a total of 16 mg per vial (overfill deliverable volume 3.5 mL at 5 mg/mL). (equivalent to 16 mg ADCT-402)

5.5.1 ADCT-402 Drug Product

ADCT-402 is a sterile formulation containing PBD-conjugated RB4v1.2 (DAR ≥ 1), RB4v1.2 (DAR = 0), and SG3249. It is provided pre-formulated in 10-mL glass vials containing approximately 16 mg ADCT-402 per vial (deliverable volume 3.2 mL at 5 mg/mL).

5.6 Management of Clinical Supplies

5.6.1 Study Drug Packaging and Storage

ADCT-402 will be supplied in a labeled 10-mL stoppered glass vial shipped to the investigational site. Once the package arrives, the receiving site pharmacy will complete the enclosed procedures to acknowledge receipt.

All study drugs must be stored in a secure area (e.g., a locked cabinet). ADCT-402 should be protected from light and stored frozen (-65°C or below). ADCT-402 should be thawed under ambient conditions.

5.6.2 Study Drug Preparation and Administration

After the vials have been completely thawed, they should be gently mixed by swirling to ensure homogeneity and visually inspected before use. The appropriate quantity of ADCT-402 will be removed from the vial with a syringe and diluted into a 50 mL IV bag containing 5% dextrose in water (D5W)/Glucose. The amount of the product to be diluted will depend on the dose level and the body mass of the patient. Once the ADCT-402 has been transferred, the bag should be mixed to ensure homogeneity of the dosing solution. The contents of the IV bag will then be administered to the patient with a dosing pump per institutional guidelines for intravenous fluid.

Additional instructions regarding study drug handling, storage, and preparation are included in the pharmacy manual.

5.6.3 Study Drug Accountability

The Investigator will maintain accurate records of receipt of all study drugs, including dates of receipt. In addition, accurate records will be kept regarding when and how much study drug is dispensed and used by each patient in the study. Reasons for departure from the expected dispensing regimen must also be recorded. All study drugs will be reconciled and retained or destroyed according to applicable regulations.

5.7 Overdose Management

An overdose is any dose of study treatment given to a patient that exceeds the dose described in the protocol. Any overdose, with or without associated AEs, must be promptly reported to the Sponsor. There are no data available to determine what the effects of overdose are and whether they can be reversed. Symptomatic treatment and standard supportive care measures for the management of any observed toxicity should be applied.

5.8 Treatment Compliance

Administration of the study treatments will be performed by the Investigator or a qualified designee; therefore, compliance will be verified by the study drug administration information.

5.9 Concomitant Treatment

All medications used within 14 days prior to Day 1 and during the treatment period are recorded in the eCRF. This will include all prescription drugs, herbal products, vitamins, minerals, and

over-the-counter medications. Any changes in concomitant medications will also be recorded in the patient's eCRF.

5.9.1 Prohibited During Study

- Other anticancer therapy with the exception of hormonal therapy for maintenance treatment of breast and prostate cancer.
- Radiation therapy is prohibited during the first cycle of therapy. After the first cycle, radiation is permitted for palliative use only if documented radiographic disease progression is ruled out first.
- Other investigational agents.
- Chronic treatment with corticosteroids (prednisone \geq 12.5 mg/day or dexamethasone \geq 2 mg/day, excluding inhaled steroids).
- Live vaccines.

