4.1.11 Long-term Follow-up

Patients who discontinue treatment for any reason other than objective disease progression will continue to be followed with scans approximately every 12 weeks from the last tumor assessment until disease progression, or initiation of new anticancer treatment. If a patient discontinues treatment for a hematopoietic stem cell transplant, the frequency of imaging will be as per the transplant center standard of care.

After documentation of disease progression or start of new treatment, patients will be contacted by telephone approximately every 12 weeks for up to 12 months after the last dose of study drug to collect survival information.

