## 4.7.3 Subsequent Anticancer Therapy or Procedure

Patients' subsequent anticancer therapies or procedures including systemic therapy, radiation, transplant, or other, along with the start date of new anticancer therapy or procedure will be collected and listed only.

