### 4.8.2 Adverse Events, Serious Adverse Events, and Deaths

#### 4.8.2.1 Analyses of adverse events

The primary focus of adverse event reporting will be on TEAEs. An adverse event (AE) will be considered to be a TEAE if it begins or worsens on or after first dose date and until 84 days (12 weeks) after the last dose date, or start of a new anticancer therapy/procedure, whichever comes earlier.

An AE occurring before the first dose or more than 84 days (12 weeks) after last dose date or after the start of a new anticancer therapy/procedure will not be included in TEAE displays, but will be listed as non-TEAEs.

If an AE date/time of onset (occurrence, worsening, or becoming serious) is incomplete, an imputation algorithm will be used to classify the AE as pre-treatment, TEAE, or post-treatment. The algorithm for imputing date/time of onset will be conservative and will classify an AE as a treatment-emergent unless there is definitive information to determine it is a non-TEAE (pre- or post-treatment).

Details on classification of AEs with missing or partial onset dates are provided in Section 6.

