### 4.9.1 Overall Response Rate

Overall response rate is defined as the proportion of patients who achieve either CR or PR as best overall response as assessed by investigators according to the Lugano Classification criteria before the start of subsequent anticancer therapy or procedure.

The order of overall response category is: CR, PR, SD, NE, PD (including disease recurrence/relapse). The overall response category will be derived based on response assessment performed on or before the start of subsequent anticancer therapy/procedure. Patients without documented subsequent anticancer therapy and/or with missing start date of anticancer therapy will be considered as not having received subsequent anticancer therapy. If a patient only has one valid disease assessment which is SD, and the assessment is within 35 days after the first dose, the overall response for this patient will be considered as NE.

The overall response rate and the corresponding 95% two-sided exact confidence interval at each dose level will be presented. Subgroup analysis may be provided for disease subtype, disease stage, double/triple hit (yes/no), bulky disease (yes/no), age group, sex, country, response to the first line and/or most recent line of prior systematic therapy (relapse: CR+PR vs. refractory: SD+PD vs. other: NE + missing), and other relevant variables.

Percent change from baseline in the sum of product of diameters (SPD) for target lesions will be presented for available data in the efficacy analysis set by dose level. These data will also be displayed as a waterfall plot, with vertical bars representing the sorted values of best percent reduction for each patient.

Tumor response and lesion measurement will be listed by assessment visit.

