#### **4.9.4 Progression-free Survival**

Progression-free survival is defined as the interval between the date of first dose and the date of disease progression (based on radiographic or clinical progression at EOT/EOS) or death, whichever occurs first. Patients who have the event after the start of subsequent anticancer therapy/procedure, or who are progression-free and alive at the time of clinical cutoff, or have unknown status, will be censored at the time of their last valid disease assessment on or before the start of subsequent anticancer therapy/procedure or clinical cut-off. When a subsequent anticancer therapy was used and progressive disease (based on radiographic or clinical progression at EOT/EOS) were observed within 6 days, they will be considered as the same visit (within the +/-6 days window) and the patient will be counted as having an event.

Patients with no post-baseline disease assessment will be censored on Day 1.

PFS will be estimated and displayed by dose levels for the efficacy analysis set using Kaplan-Meier methods (SAS® PROC LIFETEST). Patients who do not have a PFS event during or after the study will be censored. A Kaplan-Meier plot will be presented.

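### The SAP lists radiation as subsequent anticancer therapy with no exception for the on-treatment palliative radiation that the protocol permits, and it has no rule for irradiated lesions and no post-therapy cut for SPD displays

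*Protocol*

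**What the plan says.** Protocol 5.9.1 prohibits radiation in Cycle 1 and then relaxes the rule: "After the first cycle, radiation is permitted for palliative use only if documented radiographic disease progression is ruled out first". The withdrawal reasons in Protocol 4.2.1 do not name radiation.

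SAP 4.7.3 describes the therapies collected after or beyond study drug as "subsequent anticancer therapies or procedures including systemic therapy, radiation, transplant, or other, along with the start date of new anticancer therapy or procedure". That sentence uses subsequent and new for the same thing and makes no exception for palliative or on-treatment use.

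Several analyses depend on the start date of such therapy:

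- **TEAEs (SAP 4.8.2.1).** The window runs "until 84 days (12 weeks) after the last dose date, or start of a new anticancer therapy/procedure, whichever comes earlier". An AE starting "after the start of a new anticancer therapy/procedure will not be included in TEAE displays, but will be listed as non-TEAEs".
- **Laboratory, ECG and vital signs (SAP 4.8.3 to 4.8.5).** Summaries stop at that start date.
- **Best overall response (SAP 4.9.1).** Only assessments on or before that date count.
- **PFS (SAP 4.9.4).** Patients whose event comes later "will be censored at the time of their last valid disease assessment on or before the start of subsequent anticancer therapy/procedure or clinical cut-off". DOR (SAP 4.9.2) has the same trigger. The only relief is progression within 6 days of the new therapy.

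The SPD change in SAP 4.9.1 is shown for whatever data are available, with a waterfall plot "with vertical bars representing the sorted values of best percent reduction for each patient". No cut at subsequent therapy is stated there. Protocol 4.1.11 foresees imaging after transplant: "If a patient discontinues treatment for a hematopoietic stem cell transplant, the frequency of imaging will be as per the transplant center standard of care".

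**The concern.** A patient without progression can be irradiated for palliation from Cycle 2 and keep receiving ADCT-402. If the SAP's term covers that radiation, the patient's later on-drug AEs leave every TEAE table, although safety is a primary endpoint. PFS or DOR would also be censored in a patient who is still treated and progression-free. That censoring may be informative, because symptomatic patients are the ones likely to be irradiated.

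If the term does not cover it, nothing in the SAP says how an irradiated lesion enters response or SPD. The trial has no comparator, so a local radiation effect, or a transplant effect in the waterfall plot, would be credited to the drug.

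**Working it through.** The documents give no figure on this point, so the check sets the rules side by side. Short illustrations follow, with assumed dates and counts.

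**1. Can radiation occur under continued dosing?** Protocol 5.9.1 permits it after Cycle 1, and Protocol 4.2.1 attaches no stop to it. Continued dosing is an inference from these two sections; it is not stated outright.

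**2. Does the SAP's wording reach it?** SAP 4.7.3 names radiation without limiting the timing. SAP 4.6 leaves anticancer therapies out of concomitant medications, so on-treatment radiation is not handled there. The one rule linking subsequent therapy to the last dose is in SAP 6.1.1: an imputed date that falls before the last dose is moved to last dose + 1. A complete on-treatment date is not covered. Read literally, the cut applies.

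**3. Was that meant?** Probably not.

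- Protocol 4.1.9 places the End of Treatment visit after discontinuation and before new anticancer treatment.
- The schedule in Protocol 12.1.1 collects new-treatment information only at the 12-week and long-term follow-up.
- Protocol 6.3.2.2 ends AE collection at new anticancer treatment. If permitted radiation counted, sites would stop collecting AEs in a patient still being dosed.
- The imputation rule in SAP 6.1.1 points the same way.

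**4. Agreement with the protocol.** The TEAE window in Protocol 7.6.1.1 runs to last dose + 84 days with no cut at new therapy. Protocol 7.6.2.1 takes best response up to discontinuation of ADCT-402. SAP 3.3 declares only the change to the efficacy set.

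**5. Literal reading, worked example.** Assume 3-week dosing and radiation on Cycle 3 Day 1, that is 1 + 2 × 21 = Day 43. The last dose in Cycle c is on Day 1 + 21(c − 1), and the window should end 84 days later.

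- Last dose in Cycle 4: Day 64, window to Day 148. Lost: 105/148 = 71%, with 2 doses on or after the cut.
- Last dose in Cycle 6: Day 106, window to Day 190. Lost: 147/190 = 77%, with 4 doses.
- Last dose in Cycle 8: Day 148, window to Day 232. Lost: 189/232 = 81%, with 6 doses.

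For PFS, assume assessments near Days 42 and 84. Radiation on Day 30, 64 or 100 followed by a later event gives censoring on Day 1, 42 or 84.

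**6. Likely reading, response.** Suppose an irradiated lesion holds 60% of baseline SPD and disappears while the others are unchanged. SPD falls to 0.40 of baseline, a 60% reduction. This passes the 50% SPD criterion for CT-based PR in Protocol 12.2, which is one of several criteria. If one extra response resulted, ORR with the exact 95% interval of SAP 4.9.1 would change as follows. The response counts are assumed; the sizes are the Part 2 cohort sizes in Protocol 7.3. The limits are the beta quantiles B(0.025; x, n − x + 1) and B(0.975; x + 1, n − x).

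- n = 10: 4/10 = 40.0% (12.2 to 73.8) becomes 5/10 = 50.0% (18.7 to 81.3).
- n = 20: 8/20 = 40.0% (19.1 to 63.9) becomes 9/20 = 45.0% (23.1 to 68.5).

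**7. SPD displays.** Within SAP 4.9.1, response is cut at subsequent therapy and SPD change is not. This gap exists under either reading.

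**The case against.** The strongest reply is that subsequent therapy plainly means therapy after study drug. On that meaning the safety windows are right and PFS and DOR are not censored at permitted radiation. The evidence in step 3 supports this, and I accept it as the likelier intent. It does not remove the fault, because the SAP text that programmers will apply does not say so for complete dates.

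Three stronger conclusions are tempting, and the documents do not support them:

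- **That the plan is wrong whichever way it is read.** For the safety windows and for PFS/DOR censoring, the post-treatment meaning already gives a sound result.
- **That 81% of safety follow-up is lost.** That figure needs the literal reading plus assumed radiation and last-dose dates. Even then the later AEs are listed as non-TEAEs, all SAEs are listed (SAP 4.8.2.1), and deaths during the study are summarized without this cut (SAP 4.8.2.2).
- **That a 60% SPD fall makes a PR.** Response is the Investigator's Lugano assessment. It is often PET-based, on a five-point uptake scale. CT-based PR also has requirements on non-measured lesions, spleen and new lesions.

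It is also fair to say that Protocol 4.1.11 concerns imaging frequency and does not state that post-transplant SPD is recorded. The missing cut therefore matters only if those measurements reach the database. Nor does any section say that the irradiated site is recorded, so exclusion lesion by lesion may not be possible.

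**Conclusion.** The point holds as a wording fault with two smaller gaps. The SAP's literal text conflicts with its likely intent and with the protocol's own TEAE window. It would end safety summaries, best response and PFS/DOR follow-up in a patient still being dosed. Under the likely reading, shrinkage of an irradiated assessed lesion can contribute to a new CR or PR, and control of that site could lengthen PFS and DOR. The SPD table and waterfall plot lack the ORR cut.

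The overall size is unknown because the number of patients irradiated on treatment is not given. The response gap matters only if an assessed lesion is irradiated. DLT and MTD assessment is unaffected, since the DLT period is Cycle 1 and radiation is prohibited then. OS is unaffected. The study is descriptive, with no hypothesis tests. The change is still worth making, because otherwise the meaning may be chosen after open-label data have been seen. The available SAP text is incomplete between 4.1.4 and 4.4, and nothing is held against the plan on that account.

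**What to change.** All changes are to the SAP and are analytic only.

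1. Define subsequent or new anticancer therapy or procedure as therapy started after the last ADCT-402 dose. Use this definition for the TEAE, laboratory, ECG and vital-sign windows, for best response, and for PFS/DOR censoring. State that protocol-permitted on-treatment palliative radiation does not trigger the cuts. Add a sensitivity analysis that censors PFS and DOR at such radiation.
2. Apply the ORR cut-off (assessments on or before the start of subsequent therapy or transplant) to the SPD table and waterfall plot.
3. Keep the Investigator's response as the main ORR and flag patients irradiated on treatment. Add a sensitivity ORR and waterfall plot that do not count a new CR or PR first recorded after radiation. Exclude individual lesions only if the radiation site is recorded.

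The cost is a few sentences, a few more programmed flags from therapy and assessment dates, and possibly a slightly lower sensitivity ORR.
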